3.4 Safety Variables

The tolerability and safety will be assessed using the following endpoints:

- The incidence of treatment-emergent adverse events
- Changes from baseline to each time point in clinical laboratory (hematology, chemistry, urinalysis) values (some of which are also evaluated as efficacy parameters), and the occurrence of clinically significant abnormal changes
- Changes from baseline in vital signs (systolic and diastolic blood pressure, heart rate, weight, and abdominal girth) at each visit, which will also be examined as exploratory efficacy endpoints
- Changes from baseline in quantitative electrocardiogram (ECG) parameters (mean heart rate, PR interval, QRS duration, QT interval, QTcB interval, QTcF interval, RR interval)
- Time to first event of death, adjudicated non-fatal myocardial infarction (MI) or unstable angina (USA) hospitalization, adjudicated hospital admission for heart failure (HF), or adjudicated non-fatal ischemic stroke
- Time to first event of death, adjudicated non-fatal MI or USA hospitalization, adjudicated hospital admission for HF, adjudicated non-fatal ischemic stroke, or adjudicated liver event. A liver event consists of ascites, hepatic encephalopathy, variceal hemorrhage, hepatocellular carcinoma (HCC), or liver transplant
- Incidence of adjudicated severe hypoglycemia events
- Incidence of bone fracture requiring surgery or hospitalization

4 PHARMACOKINETIC/PHARMACODYNAMIC VARIABLES

Steady-state trough measurement will be made for MSDC-0602 and MSDC-0597 (a major pharmacologically active metabolite), at Study Visits 2, 4, 5, 6, and 7 (Days 30, 90, 180, 270, 360). The details for the population PK analysis will be covered in a separate Pharmacokinetic Analysis Plan.

5 ANALYSIS POPULATIONS

Final decisions regarding the assignment of subjects to analysis sets will be made during the Validity Review Meeting and documented in the Validity Review Report prior to final database lock and unblinding for the final analysis. **Data from sites with serious GCP or quality concerns may be excluded from the analyses.** The Sponsor will provide a list of such sites, and during the review it will be decided from which analyses and from which sites data should be excluded.

5.1 Enrolled Set

The Enrolled set includes all subjects who signed informed consent.

5.2 Modified Intent-to-treat Analysis Set

The modified Intent-to-Treat (mITT) analysis set includes all subjects who are randomized and who receive at least one dose of study drug. Baseline measures and post-baseline assessments through 14 days after the last dose of study drug will be included in the analyses unless stated otherwise below. Subjects in the mITT will be analyzed as randomized regardless of treatment received. This means that subjects who are randomized who receive the incorrect study drug (i.e., not the study drug to which they were randomized) will be analyzed for efficacy under mITT as in the treatment group to which the subject was randomized. The primary population for efficacy analyses is the mITT.

5.3 Safety Analysis Set

The Safety analysis set (SAF) includes all subjects who are randomized and received at least one dose of study drug. SAF will be used in the analyses of all safety endpoints. Subjects will be included in the analyses according to the actual treatment they received. If a subject incorrectly receives more than one dose of study drug, the subject will be analyzed in the treatment group corresponding to the highest dose received. Baseline measures and post-baseline assessments through 14 days after the last dose of study drug will be included in the analyses.

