6 STUDY DESIGN

6.1 Summary of Study Design

This is a double-blind, randomized, placebo-controlled study of three oral dose levels of MSDC-0602K. Subjects will be screened for eligibility up to 42 days in advance of randomization (between Days -42 and -1). Subjects will be randomized into 1 of 4 treatment groups based on a stratification criteria of presence Type 2 DM (Yes/No), use of Vitamin E \geq 400 IU (Yes/No), and fibrosis score (F1 or \geq F2) and will receive single daily doses of MSDC-0602K (62.5, 125 or 250 mg), or placebo for one year (360 days). Approximately 380 subjects will be randomized to achieve 85 completed subjects in each of the 4 treatment groups. The number of subjects who have a fibrosis score of F1 will be no greater than 50% of each group in order to best inform the design of the Phase 3 clinical trial.

- Male or female subjects with NASH and fibrosis should have an interpretable liver biopsy within 9 months prior to randomization and at the end of study treatment at Visit 7. Double-blind study drug will be dispensed for daily administration starting at Study Visit 1. Subsequent study visits will occur on Days 30 (1 month), 60 (2 months), 90 (3 months), 180 (6 months), 270 (9 months), 360 (12 months) and a 14-day follow-up visit on Day 374. Subjects will self-administer study drug once daily throughout the treatment period through the Day 360 visit. Site personnel will contact subjects every month to inquire about safety, adverse events and serious adverse events.

Blood samples will be collected for trough level assay of MSDC-0602 and major metabolite MSDC-0597 concentrations. Fasting blood samples will also be collected for analysis of

biomarkers and for safety chemistry/hematology laboratory testing at all outpatient visits. Urine samples will be collected for urinalysis quarterly throughout the study.

Subjects will return to the clinic for a Follow-Up visit approximately 2 weeks after the final dose (Day 374, Visit 8) for blood sampling. A complete physical examination will be performed at Screening and at the Follow-up visit on Day 374, and a limited physical examination will be performed at all other study visits.

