- Study drug (3 bottles of 33 capsules from the assigned kits) will be dispensed

6.2.8 Study Visit 6, Month 9

Subjects will be instructed to report to the clinic on the morning of Day 270 following a minimum 10-hour fast and without having taken their morning dose of study drug. Subjects should return the unused study drug. The following procedures will be performed for all subjects at Study Visit 6 (Day 270 \pm 7 days):

- Limited physical examination
- Vital sign measurements
- Assess compliance to diet (Y/N) and alcohol intake (Y/N)
- Blood sample for clinical chemistry and hematology laboratory testing
- Liver function tests
- Blood sample for trough PK analysis of MSDC-0602 and MSDC-0597
- Urine sample for urinalysis
- Monthly phone calls to inquire about adverse events and serious adverse events
- Notation of any change in concomitant medication use
- Documentation of any AEs
- Study drug (3 bottles of 33 capsules from the assigned kits) will be dispensed

6.2.9 Study Visit 7, Month 12

Subjects will be instructed to report to the clinic on the morning of Day 360 following a minimum 10-hour fast before taking their morning dose of study drug. Subjects should return the unused study drug. The following procedures will be performed for all subjects at Study Visit 7 (Day 360 \pm 7 days):

- Limited physical examination
- Vital sign measurements
- 12-lead ECG
- Assess compliance to diet (Y/N) and alcohol intake (Y/N)
- Transient elastography of liver fibrosis (FibroScan)
- Liver biopsy
- Clinical chemistry and hematology laboratory testing
- Liver function tests
- Urine sample for urinalysis
- HMW adiponectin, hsCRP, CK-18 [M30 & M65], osteocalcin and serum CTX

- Calculation of Fibrosure, ELF score, and its individual components (HA, PIIINP, TIMP-1), APRI, FIB-4 index, and Pro-C3
- NMR analysis of lipoprotein particle size
- Future miRNA and additional biomarkers of interest testing
- Trough PK analysis of MSDC-0602 and MSDC-0597
- Notation of any change in concomitant medication use
- Documentation of any AEs

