6.2.10 Study Visit 8, Day 374 (Follow-Up Visit)

The following procedures will be performed for all subjects at the Follow-Up Visit (Study Visit 8, Day 374 \pm 3 days):

- Complete physical examination
- Vital sign measurements
- 12-lead ECG
- Pregnancy Test (females only)
- Clinical chemistry and hematology laboratory evaluations
- Urine sample for urinalysis
- Documentation of any AEs

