6.2.3 Imputation for Primary Endpoint

Sensitivity analyses will be performed on the primary endpoint using two different imputation methods. The sensitivity analyses will include all subjects who were randomized and who received at least one dose of study drug. Two approaches will be used to impute or substitute missing response at 12 months. Post-baseline observations that have been excluded from the primary analysis due to biopsies taken more than 14 days after last dose of study drug will be treated as missing and imputed or substituted as well.

When using multiple imputation, missing baseline and/or post-baseline values needed to determine response at 12 months will be imputed multiple times to account for the uncertainty about the true values to impute. To this end, each of the four categorical variables underlying the response definition of the primary endpoint will be imputed if missing, using the following categories:

- Steatosis: 0, 1, 2, 3
- Lobular inflammation: 0, 1, 2, 3
- Ballooning: 0, 1, 2
- Fibrosis score: 0, 1, 2, 3, 4

Using the SAS[®] procedure PROC MI 10 imputed data sets will be generated. The regression model will be adjusted for the corresponding baseline values and will further use presence of diabetes mellitus, Vitamin E use ≥ 400 IU, age, and sex as covariates.

An example of the SAS[®] code to be used is below:

```
proc mi data= out=<output dataset> seed=1234 nimpute=10
  minimum=<...> maximum=<...> round=<...>;
var <12 months steatosis> <baseline steatosis>
  <12 months lobular inflammation> <baseline lobular inflammation>
  <12 months ballooning> <baseline ballooning>
  <12 months fibrosis score> <baseline fibrosis score>
  <presence of diabetes mellitus> <Vitamin E use  $\geq 400$  IU> <sex><age at baseline>;
run;
```

The 10 multiple imputed datasets will be used separately in the statistical analysis model and the resulting odds ratios and 95% CIs will be combined via Rubin's rules (using PROC MIANALYZE) to provide a global estimate of the odds ratio with a corresponding 95% CI and p-value.

As a second sensitivity analysis of the primary endpoint, subjects with missing response data at 12 months will be included as non-responders. Similar to above, this sensitivity analysis will include all subjects who were randomized and who received at least one dose of study drug.

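### The 14-day safety cut-off makes no allowance for the Visit 7 and Visit 8 windows and conflicts with SAP 6.1 and 7.9, so in-window follow-up measurements can drop out of the by-visit safety summaries

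*SAP*

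**What the plan says.** **The cut-off.** For the safety set, SAP 5.3 states: "Baseline measures and post-baseline assessments through 14 days after the last dose of study drug will be included in the analyses". Protocol 11.2 carries the same limit. The mITT definition in SAP 5.2 uses the same 14 days but leaves room for exceptions: "through 14 days after the last dose of study drug will be included in the analyses unless stated otherwise below". SAP 5.3 has no such clause and no visit-window allowance. SAP 6.2.3 shows the limit working as an exclusion for histology, where it refers to observations "excluded from the primary analysis due to biopsies taken more than 14 days after last dose of study drug".

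**The visits.** Protocol 6.2.10 lists the procedures "performed for all subjects at the Follow-Up Visit (Study Visit 8, Day 374", with a window of ± 3 days. Protocol 6.1 also anchors this visit to dosing: "Subjects will return to the clinic for a Follow-Up visit approximately 2 weeks after the final dose (Day 374, Visit 8) for blood sampling". Visit 7 is Day 360 ± 7 days (Protocol 6.2.9 and Table 1).

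**The last dose.** Protocol 6.1 says: "Subjects will self-administer study drug once daily throughout the treatment period through the Day 360 visit". Protocol 6.2.9 has subjects attend Visit 7 "following a minimum 10-hour fast before taking their morning dose of study drug" and hand back unused drug. The text does not settle whether the final capsule is taken on the Visit 7 day or the day before.

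**The by-visit summaries.** SAP 6.1 analyses scheduled visits under the investigator's nominal label. It maps unscheduled ones to Follow-up from Day 368 onward, with no upper limit. SAP 7.9.2 (laboratory) and 7.9.3 (vital signs and weight) refer to that windowing. SAP 7.9.4 summarises ECGs by visit, and SAP 7.9.5 presents edema grades at every visit after baseline.

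**The concern.** Two rules apply to the same measurements and give different answers. Under SAP 6.1 and 7.9, a Visit 8 haemoglobin taken 17 days after the last dose belongs in the Follow-up column. Under SAP 5.3 it does not enter the safety analyses. A programmer could follow either rule and be able to cite the SAP.

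Following SAP 5.3 literally has two consequences. Measurements taken fully in accordance with the protocol are left out of the summary tables. The omission also depends on drug-free time: intervals up to 14 days stay and longer ones go, so the Follow-up column describes the least washed-out subjects. For completers, Visit 8 is the only scheduled look at laboratory values, ECG, vital signs, weight and edema off drug, and hence the only planned summary of whether on-treatment changes recede.

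For biopsies, the SAP covers the loss from the 14-day limit with a sensitivity analysis that uses all observed results (SAP 7.8.1). The safety measurements have no counterpart.

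**Working it through.** **The plan's own timing.** 42 + 360 + 14 = 416 days, and 360 + 14 = Day 374. Both match Protocol section 10 and the schedule. The nominal Visit 8 is thus exactly 14 days after a Day 360 last dose, which is on the boundary with no slack.

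**Inputs**
- Visit 7: Days 353 to 367 (360 ± 7).
- Visit 8: Days 371 to 377 (374 ± 3).
- Cut-off: gap of at most 14 days.
- Last dose: reading A, the Visit 7 day; reading B, the day before.
- Planned completers: 340 (Protocol section 5).

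**Formula.** With e7 and e8 the deviations of the two visits from target, gap = (374 + e8) − (360 + e7) = 14 + e8 − e7 under A, and one day more under B. A visit is lost when e8 > e7 under A, or e8 ≥ e7 under B.

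**Range of in-window gaps**
- A: 371 − 367 = 4 to 377 − 353 = 24 days.
- B: 371 − 366 = 5 to 377 − 352 = 25 days.

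**Share lost.** The documents give no distribution of visit days, so each row is an assumption.

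| Assumed timing | A | B |
|---|---|---|
| Both visits even over their windows (15 × 7 = 105 pairs) | 49/105 = 46.7% | 56/105 = 53.3% |
| Visit 7 on Day 360, Visit 8 even over 7 days | 3/7 = 42.9% | 4/7 = 57.1% |
| Visit 7 on Day 360, Visit 8 clustered on target (normal weights, SD 1 day) | 30.0% | 70.0% |
| Both visits exactly on target | 0% | 100% |

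The pair counts are sums over e8 = −3 to 3. Under A, each e8 has e8 + 7 values of e7 below it, total 49. Under B, each has e8 + 8 values at or below it, total 56.

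The two even-spread rows give 42.9% to 57.1%, or 146 to 194 of 340 completers. If Visit 8 is booked 14 ± 3 days from the actual last dose and spread evenly, the share is again 3/7 = 42.9%. The 100% extreme does not need reading B: if every Visit 7 fell on Day 353, the smallest gap under A would be 371 − 353 = 18 days.

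**Would a 3-day allowance be enough?** With a 17-day limit and both visits even, 28/105 = 26.7% (A) or 35/105 = 33.3% (B) are still lost. Covering every in-window Visit 8 takes 24 days under A and 25 under B.

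**The case against.** The strongest reply is that no data need be lost. The SAP sections that generate the laboratory and vital-sign tables invoke SAP 6.1, which would keep a nominal Visit 8. SAP 7.9.6 to 7.9.8 restate the 14-day limit where it is wanted (cardiovascular and liver events, severe hypoglycaemia, fractures), so its absence from 7.9.2 to 7.9.5 could be deliberate. This is a fair reading, but the SAP does not state it. SAP 5.3 covers all safety endpoints and contains no exception. What stands is that there is a conflict, not a certain loss.

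A reader might infer more than the documents support:

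- *That about half of completers will lose the visit.* The figure depends on an assumed spread of visit days, as the table shows.
- *That Visit 8 is tied only to study day.* Protocol 6.1 also places it about two weeks after the final dose. Booking on that basis narrows the gap to 11 to 17 days, but the cut-off still falls in the middle of that range.
- *That a subject exactly on schedule is dropped.* This needs a Day 359 last dose. Protocol 6.1 has dosing run through the Day 360 visit, and on that reading the subject is at 14 days and is kept.

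The impact is also limited. All collected data are listed (SAP 7.1). Adverse events are classified by onset, and later ones are listed separately (SAP 7.9.1). Visit 7 data are normally unaffected. The cut-off is identical in all four arms, so no between-arm bias is shown. Reversal after stopping is not a stated objective or endpoint. The reversible animal findings in Protocol 2.2.2 come from 13-week studies whose cited titles include a 4-week recovery period, so they do not show what a visit at about two weeks would reveal. All of this stands. It limits the importance of the point but does not remove the conflict.

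**Conclusion.** The point holds as a conflict with a measurable consequence. The 14-day limit in SAP 5.3 and Protocol 11.2 ignores both visit windows and disagrees with SAP 6.1 and 7.9. If SAP 5.3 governs, in-window Visit 8 laboratory, vital-sign, ECG and edema data leave the by-visit summaries whenever the gap exceeds 14 days, and the longest drug-free intervals go first.

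The size is roughly 43% to 57% of completers if visit days are spread evenly. It depends on that assumption and on which day the last dose falls, and the windows themselves permit 0% to 100%. The gap ranges of 4 to 24 and 5 to 25 days follow directly from the stated windows. The effect is confined to descriptive summaries of one visit. Efficacy, adverse-event classification and listings are untouched. The sponsor should correct it because the remedy is cheap and the visit has no scheduled substitute for completers.

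**What to change.** Add one sentence to SAP 5.3, along these lines:

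*Nominal Visit 8 assessments made within 25 days of the last dose are included in the by-visit safety summaries; the 14-day limit applies to all other post-baseline safety assessments.*

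Label the Follow-up column off-treatment and summarise days since last dose beside it by treatment group. The limit of 25 days is Day 377 minus Day 352, the largest gap that the windows allow. If the last dose is on the Visit 7 day, 24 is enough, so 25 covers both readings without having to settle the dosing question. State whether unscheduled assessments that SAP 6.1 maps to Visit 8 follow the same limit.

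Because Protocol 11.2 contains the same 14-day sentence, record the departure in SAP Section 8.

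The cost is one sentence, one Section 8 entry, a column label and one extra summary. Data collection, dosing and visit timing do not change. The small downside is that the Follow-up column mixes drug-free intervals up to 25 days, which the label and the days-since-last-dose summary make visible.

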5.4 Per Protocol Analysis Set

The per-protocol analysis set (PPS) includes all subjects in mITT without major protocol deviations. Major protocol deviations are defined as those deviations considered to have a major effect on the collection or interpretation of the primary efficacy endpoint. Section 5.4.1 details the classification of deviations. Additionally, subjects assigned to the active treatment groups with 2 or more samples in which PK trough levels of both the parent drug (MSDC-0602K) and its metabolite are below the level of detection will be assumed to have been non-compliant and may be excluded from the PPS, and/or all subjects at sites where the majority of subjects assigned to active treatment appear to have been non-compliant based on trough levels may be excluded. Identification of all subjects and measures to be included in the PPS analyses will be determined before the final database lock and unblinding for the final analysis.

The PPS will be used as an additional sensitivity analysis for key efficacy endpoints. PPS subjects will be analyzed as randomized regardless of treatment received.

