2.2 Overall Study Design

This is a randomized, double-blinded, placebo-controlled multiple-dose phase II study to evaluate the safety, tolerability and efficacy of three dose levels of MSDC-0602K in subjects with non-alcoholic steatohepatitis (NASH).

Approximately 380 subjects will be randomized at 1:1:1:1 ratio to the following four treatment arms, and the drug is taken orally once per day for 12 months:

- MSDC-0602K 62.5 mg
- MSDC-0602K 125 mg
- MSDC-0602K 250 mg
- Placebo

Randomization will be stratified by:

- Presence of Type 2 diabetes mellitus (T2DM) (Yes/No)
- Use of Vitamin E \geq 400 IU (Yes/No)
- Fibrosis score (F1 vs. F2/F3)

This study will comprise a maximum 42-day Screening period, a treatment period of 360 days and a 14-day follow-up period. The total duration of the study for each subject will be up to 416 days, including follow-up.

The primary efficacy endpoint will be assessed at 12 months after randomization. Visits to the clinic will be at baseline, 1, 2, 3, 6, 9, and 12 months, with one follow-up visit at study day 374.

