2.3 Sample Size and Power

Each active treatment group will be compared with the placebo group at the two-sided 0.05 significance level; 85 subjects per arm provides approximately 80% power to detect a difference in the proportions of subjects achieving the primary efficacy endpoint of 39.5% in any MSDC-0602K group versus 20% response rate in the placebo group. These response rates are similar to effects reported after 18 months daily treatment with 45 mg pioglitazone (58% response) or placebo (17% response) in subjects with pre-diabetes or T2DM (Cusi 2014); after 96 weeks daily treatment with 30 mg pioglitazone (34% response) or placebo (19%) in non-diabetic adults with NASH in the PIVENS study (Sanyal 2010); and in the GOLDEN study, after 52 weeks daily

treatment with 120 mg elafibranor (32% response) or placebo (21%) in the subset of NASH subjects with a baseline NAS ≥ 4 (Ratziu 2016). Assuming 10% of subjects will not complete the 12-month assessment due to early dropout, 380 subjects will be randomized to the study. Sample size calculations were made using nQuery Advisor® (Statistical Solutions Ltd., Boston, MA, USA).

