		
Thus, subjects will be reviewed for exclusion if NAS < 4, or score of 0 in any component of NAS, or fibrosis score of F0 or F4.
 
5. Subjects with type 2 diabetes mellitus (DM) must be under stable and reasonable control, defined as under a healthcare provider's care for DM with glycosylated hemoglobin [HbA1c] ≤ 9.5%. Subjects taking permitted anti-diabetic therapies (metformin, GLP-1 agonists, SGLT2 inhibitors, sulfonylureas or DPP4 inhibitors) must be on stable doses for a period of at least 3 months prior to randomization.
 
Manual review will be performed for identifying subjects who violate the above I/E criteria, including review of prohibited changes reported for the 3 months prior to randomization (in reference to inclusion criterion #5 above).

Prohibited Medication Use	Subjects who took medications that are not permitted during the study	
Programmatic identification of subjects with CRF-reported post-randomization use of PPARγ agonist, insulin, ursodeoxycholic acid, paclitaxel, phenytoin, warfarin, celecoxib, tolbutamide or repaglinide; and subjects with reported protocol deviations related to prohibited medication use.
 
Manual review of blinded concomitant medications listing to identify subjects with prohibited changes post-randomization in therapeutic agents for diabetes. The medical monitor and Sponsor will review the listing and note any prohibited changes in these glycemic control medications; these subjects may be excluded from the PPS.

Non-compliance During the Study	Subjects who had low study drug exposure and compliance	
Programmatic check of estimated compliance based on the study drug administration data, and programmatic identification of subjects assigned to an active treatment group with parent drug (MSDC-0602K) or MSDC-0597 (major metabolite) trough levels below the detection threshold at two or more visits.
 
Manual review will be performed to identify subjects with compliance less than 80% based on study drug administration data (Section 7.7.2) and/or other compliance issues identified by sponsor.

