8 CHANGES FROM PROTOCOL-SPECIFIED ANALYSES

The specialty biomarkers to be analyzed were changed following finalization of the protocol. The following biomarker described in the protocol will not be analyzed: CK-18 [M30]. Changes from baseline in biomarkers and indirect measures of apoptosis and liver fibrosis at 6 months were added as pre-specified exploratory efficacy endpoints.

The exploratory endpoint “Changes from baseline relative to placebo at 12 months in the pathologist’s general impression” has been corrected to reporting the general impression as provided by the central histopathologist: NASH diagnosis 1) confirmed, or 2) cannot be confirmed. While the local pathologists provide the information as initially planned in the protocol, this is not available from the central histopathologist.

The last exploratory endpoint “Changes from baseline relative to placebo in subjects with PNPLA3 variants and other genotypes” has been removed from the list as it is not an endpoint per se but refers to subgroup analyses of efficacy endpoints with respect to genetic variants (see Section 7.8.3).

The definition of the per protocol analysis set was expanded to allow possible exclusion of subjects based on trough levels of study drug and its metabolite.

For the derivation of treatment compliance, the last dose date will be used instead of last dose date +14 days to define the end of the treatment period if study treatment was discontinued early. The derivation of compliance measures per treatment period as well as production of listings and/or presentation of summary statistics of per-period and of overall compliance will be omitted. The rationale for these changes is that because capsule counts are known to be unreliable and despite our best efforts to clean the data there are still discrepancies that cannot be resolved.

The methods for efficacy analysis have been clarified. Due to the expected highly unequal marginal distribution of the stratification factor “use of Vitamin E \geq 400 IU” (Yes vs. No) this factor was removed from all logistic regression models (except for the corresponding subgroup analysis).

The pairwise comparisons of active treatment versus placebo through CMH tests have been revised to only include stratification for presence of diabetes mellitus as to avoid overly sparse cross-classification frequencies of the originally included stratification factors, treatment, and outcome.

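### The trough-level exclusion acts on individual subjects in the active arms only, so the per-protocol set selects on adherence more strictly in those arms than in placebo

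*SAP*

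**What the plan says.** SAP 5.4 provides that "subjects assigned to the active treatment groups with 2 or more samples in which PK trough levels of both the parent drug" and its metabolite are undetectable may be left out of the PPS. It adds a site-level version: if most active subjects at a site look non-compliant on trough levels, every subject there may be left out, placebo included.

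The deviation table in SAP 5.4.1 repeats the restriction to active arms. It calls for "programmatic identification of subjects assigned to an active treatment group with parent drug (MSDC-0602K) or MSDC-0597" undetectable at two or more visits. SAP 7.7.3 likewise flags only active subjects as potentially non-compliant.

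SAP section 8 discloses the change: "The definition of the per protocol analysis set was expanded to allow possible exclusion of subjects based on trough levels". It does not mention that the subject-level rule acts on three arms of four.

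The adherence check open to every arm is the review of subjects below 80% capsule-count compliance (SAP 5.4.1 and 7.7.2), with any other compliance issue the sponsor notes. Section 8 describes capsule counts as unreliable and drops their listings and summaries.

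The PPS is supportive. The primary analysis uses the mITT set (SAP 5.2 and 7.8.1).

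**The concern.** A drug level can reveal a non-taker only where there is drug to find. Even if the rule were worded consistently and applied without error, it would remove hidden non-takers from the active arms and leave their placebo counterparts to a weaker check. PPS membership then depends on assigned arm through something other than the subject's own conduct.

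People who do not take their capsules may also differ in diet, visit attendance and prognosis. If they respond less often, removing them mainly from the active arms raises the active response rate with no help from the drug. A sensitivity analysis is meant to show whether the primary result is robust, and one that leans towards the drug does this poorly. SAP 7.8.1 runs all four primary-endpoint methods in the PPS, and SAP 7.8.2 uses it to support the secondary endpoints.

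**Working it through.** **The plan's own figure.** SAP 2.3 states "Each active treatment group will be compared with the placebo group at the two-sided 0.05 significance level", that "85 subjects per arm provides approximately 80% power", and rates of "39.5% in any MSDC-0602K group versus 20% response rate in the placebo group". For the uncorrected two-proportion test:

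- Mean rate = (0.395 + 0.20)/2 = 0.2975.
- z = [0.195 × √85 − 1.960 × √(2 × 0.2975 × 0.7025)] / √(0.395 × 0.605 + 0.20 × 0.80) = (1.798 − 1.267)/0.632 = 0.840.
- Power = 79.96%, which agrees with the plan. The planned difference is 39.5 − 20 = 19.5 points.

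The documents give no figure for per-protocol bias, so the rest is a model.

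**Model.** The drug is inert, with 85 subjects and a true response of 20% in every arm. The 85 and the 20% come from the SAP; the next three inputs are assumptions.

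- f: share of non-takers in each arm, 10% or 20%.
- r0: response in non-takers, 0% or 10%.
- c: share of placebo non-takers removed by capsule count, 0 or 0.5.

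All active non-takers are removed, which is the most the rule could do.

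- Taker response, equal to the active PPS rate: pt = (0.20 − f × r0)/(1 − f).
- Placebo PPS rate: [(1 − f) × pt + f(1 − c) × r0]/(1 − f × c), which is 0.20 when c = 0.
- Spurious difference: active minus placebo = [f(1 − c)/(1 − f × c)] × (pt − r0).

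**Worked case, f = 20%, r0 = 0, c = 0.**

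- pt = 0.20/0.80 = 0.25, so the difference is 0.25 − 0.20 = 5.0 points.
- The PPS sizes are 68 active and 85 placebo, with a pooled rate of 34/153 = 0.222.
- Standard error under the null: √[0.222 × 0.778 × (1/68 + 1/85)] = 0.0676, so the critical difference is 1.96 × 0.0676 = 0.1326.
- Standard error under the model: √(0.25 × 0.75/68 + 0.20 × 0.80/85) = 0.0681.
- Chance of a result favouring active: Φ[(0.05 − 0.1326)/0.0681] = Φ(−1.21) = 11.3%. The opposite tail adds 0.4%, giving 11.6% two-sided.

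**All cases.** Differences are in points. Errors are two-sided, with the part favouring active in brackets.

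| f | r0 | Active PPS rate | Difference, c = 0 | Error, c = 0 | Difference, c = 0.5 | Error, c = 0.5 |
|---|---|---|---|---|---|---|
| 10% | 10% | 21.1% | +1.1 | 5.4% (3.7%) | +0.6 | 5.1% (3.1%) |
| 10% | 0% | 22.2% | +2.2 | 6.4% (5.4%) | +1.2 | 5.4% (3.7%) |
| 20% | 10% | 22.5% | +2.5 | 6.7% (5.7%) | +1.4 | 5.5% (4.0%) |
| 20% | 0% | 25.0% | +5.0 | 11.6% (11.3%) | +2.8 | 6.8% (5.9%) |
| 10% or 20% | 20% | 20.0% | 0 | 5.0% (2.5%) | 0 | 5.0% (2.5%) |

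**Sign.** If non-takers responded better, say r0 = 30% with f = 20%, then pt = (0.20 − 0.06)/0.80 = 0.175. The difference is 0.20 × (0.175 − 0.30) = −2.5 points.

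**Three doses against one placebo arm.** In a simulation of 300,000 trials, the chance that at least one dose looks significantly better in the PPS is 6.3% with no exclusions. With f = 20% and c = 0 it is 14.0% at r0 = 10% and 25.0% at r0 = 0. With c = 0.5 these fall to 9.6% and 13.8%.

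**Symmetric exclusion.** If non-takers left every arm equally (c = 1), the difference is 0 and the two-sided error is 5.0%.

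**The case against.** A reader might infer that the PPS sets active takers against the whole placebo group. The documents do not support that. Placebo subjects can leave through the below-80% capsule review, eligibility failures, prohibited medication, other deviations and the site-level rule. This stands, though only the adherence routes offset the bias, and the main one rests on counts the SAP distrusts.

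Exclusion is also discretionary, so removing every active non-taker is an upper bound. This stands too, but discretion based on a subject's own trough levels exists only for active subjects and so does not restore balance.

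The size is assumed throughout. With an inert drug, a response of 0–10% in non-takers against 21–25% in takers needs a large prognostic gap from behaviour alone. The group may also be small: the 14-day limit after last dose already removes late biopsies of declared early stoppers in every arm. What remains is subjects with two or more undetectable samples and an in-window biopsy who pass capsule review. For scale, the standard error of a difference at 85 per arm and 20% response is √(2 × 0.20 × 0.80/85) = 6.1 points, so 1.1 to 5.0 points is about 0.2 to 0.8 standard errors. All this limits the size but does not remove the asymmetry.

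Finally, a reader might think placebo samples are never examined for drug. SAP 7.7.3 does not confine the trough listing to active arms, protocol 11.3.3.3 summarises concentrations by treatment group, and SAP 5.4.1 checks misallocation by bottle number. No further placebo check is needed.

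**Conclusion.** The point holds in a bounded form. The subject-level trough rule has no placebo counterpart, so the PPS selects on adherence more strictly in the active arms and can show a difference for an inert drug when non-takers have a different prognosis. Under the stated assumptions the spurious difference is 1.1 to 5.0 points if no placebo non-taker is removed, and 0.6 to 2.8 points if capsule counts catch half of them.

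These figures rest on a non-taker share and response rate that the documents do not supply, and on removal of all active non-takers. They show what could happen and do not predict this trial.

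It would be tempting to conclude that the trial's main result is at risk. It is not: the primary mITT analysis and its further mITT sensitivity analyses do not use trough levels. Nor is adding the rule after the protocol a fault in itself, since SAP section 8 discloses it. The change is worth making because the PPS is offered as support for the primary result.

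**What to change.** Define PPS membership only by criteria that apply in all four arms: capsule-count compliance, eligibility, prohibited medication and other deviations. Move the trough-based exclusions to a separate analysis, labelled exploratory and shown next to the PPS result. Wherever the rule is kept, use one wording: SAP 5.4 requires parent and metabolite both to be undetectable, while SAP 5.4.1 accepts either, which can exclude more active subjects.

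Optionally, add a complier-average estimate: the mITT difference in response rates divided by the proportion of active subjects with drug detected. State its assumptions: assignment has no effect in non-takers, drug detected has a fixed definition that also covers partial takers, and the mITT contrast uses observed data only and so is not a full randomised comparison.

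The cost is SAP wording and one extra run on data already collected. The downside is that the PPS keeps active non-takers whom capsule counts miss, which dilutes it in proportion to their share. If all of them stayed, the effect in takers were 19.5 points and there were none in non-takers, the loss would be 0.10 × 19.5 = 1.95 points at 10% and 0.20 × 19.5 = 3.9 points at 20%. That is not negligible, but it pulls a real effect towards zero and does not create a difference for an inert drug.
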